#### **5.8 STUDY MEDICATION ACCOUNTABILITY AND RETENTION**

Intercept Pharmaceuticals, Inc.'s representative will send study medication to the trial sites under appropriate storage conditions. All shipments of study medication should be unpacked and the contents reviewed immediately upon receipt. If it is not possible to verify the contents immediately, they must be stored at controlled room temperature until verification of the contents is possible (ideally, within 1 business day from receipt). The pharmacist or designee should verify the study medication

against the shipment documentation. The pharmacist or designee should contact the designee of Intercept Pharmaceuticals immediately to report any concerns regarding the shipment.

All study medication will be provided for use only in this trial and is not to be used for any other purpose. The investigator or designee will maintain a full record of study medication accountability, including records of individual patient dispensing and final return or disposition.

The 'Clinical Research Associate' (CRA), will review accountability records against study medication dispensed and that remaining in stock, during on-site monitoring visits and when the trial is completed, or if it is prematurely terminated. The CRA will retrieve documentation detailing and confirming the return or destruction of the study medication.

## **5.9 TRIAL OR SITE TERMINATION**

The TREAT consortium reserves the right to terminate the trial at any time. It is normal procedure to review the emerging clinical and safety data. As a result of such a review or a recommendation by the DSMC, it may be necessary to stop the trial before all patients have completed the trial.

It is the responsibility of the individual site's PI to report to their Institutional Review Board (IRB) of discontinuation of the trial and the reason for doing so in a timely fashion according to institutional policies.

## **6. TRIAL PROCEDURES**

### **6.1 SCREENING**

#### **6.1.1 Informed Consent**

The investigator or designee will explain the nature, purpose and risks of the trial to the patient and will provide him/her with a copy of the written information and informed consent form (ICF). The patient will be given sufficient time to consider the trial before deciding whether or not to participate. The patient will be informed that participation is voluntary and that her/his future medical treatment will not be compromised by participation in the trial and that s/he can withdraw from the trial at any time. The patient must be willing and able to provide written informed consent before entering the trial. The investigator or a medically qualified designee is responsible for administering and documenting the written informed consent of the patient.

#### **6.1.2 Patient Identification Assignment**

After the patient has met eligibility criteria and enrolls into the study, the patient will be assigned a unique 5 digit ID number. This 5 digit number will be used to identify the participant throughout the trial and during the data analysis.

## **6.2 VISIT PROCEDURES**

Patients should be instructed to fast overnight (at least 8 hours) immediately prior to all at-clinic visits, including the Screening Visit. While fasting, water is permitted.

### **6.2.1 Screening Period**

The screening period will consist of  $\leq 8$  weeks prior to the randomization visit (Day 0). During the screening period, participants' eligibility criteria must be confirmed. Participants must sign an informed consent prior to initiating any of the screening procedures. Patients who do not fulfill all eligibility criteria cannot continue in the protocol (screening failures).

Screening period procedures are as follows:

- The participant is to review and sign the informed consent document. Informed consent must be obtained from the patient before performing any trial related procedures, including screening procedures
- Verify inclusion and exclusion criteria for eligibility
- Assess Liver Score: MELD
- Collect medical history including the alcohol consumption specifics
- The participant is to complete the AUDIT, NIAAA and Timeline Followback Questionnaires
- Perform a physical examination, including height and weight
- Record vital signs
- Record prior (within 30 days of Day 0) and current concomitant medications
- Perform a standard 12-lead electrocardiogram (ECG)
- Assess availability of liver biopsy samples (if applicable) which may have been obtained as part of standard of care
- Obtain blood samples for serum chemistry, hematology and coagulation tests
- Perform a serum pregnancy test in females of childbearing potential
- The subject should be reminded that fasting (8 hours) is required prior to his/her next visit.

### **6.2.2 Day 0 Procedures (Randomization) – Must present after at least 8 hours of fasting**

- Collect medical history including the alcohol consumption specifics
- Perform a physical examination

- Record vital signs
- Alcohol consumption history – Timeline Followback Questionnaire
- Assess and record any pretreatment emergent AEs
- Record prior (within 30 days of Day 0) and current concomitant medications. Ascertain that participant is not receiving concomitant systemic corticosteroids on the day of randomization
- Perform a urine pregnancy test in females of childbearing potential
- Confirm inclusion and exclusion criteria for eligibility
- Assess Liver Scores: MELD, Child Pugh and Discriminant Function
- Randomize the patient only if s/he meets all inclusion criteria and no exclusion criteria
- Obtain blood samples for serum chemistry, hematology and coagulation tests
- Obtain blood samples for special investigations as outlined in section 3.2
- Obtain blood and stool samples for specimen banking as outlined in section 3.2.
- Dispense study medication and instruct the patient to begin dosing on the day after the Day 0 visit (i.e., on Day 1) and to take study medication with water, approximately 30 minutes prior to breakfast. Instruct the patient to swallow the tablet whole; s/he must not chew, divide, or crush the tablet.
- The subject should be reminded that fasting (8 hours) is required prior to his/her next visit. The subject should not take study medication on the morning of the next clinic (D14) visit as s/he will dose at the clinic.

### **6.2.3 D7 Procedures ( $\pm$ 1 days)**

- This consists of a telephone visit where the participant will be inquired about his/her well-being, compliance with IP, concomitant medications and alcohol use.
- The subject should be reminded that fasting (8 hours) is required prior to his/her next visit. The subject should not take study medication on the morning of the next clinic visit (D14) as s/he will dose at the clinic.

Ascertain that participant is not receiving concomitant systemic corticosteroids

### **6.2.4 D14 Procedures ( $\pm$ 2 days) - Must present after at least 8 hours of fasting**

- Perform a physical examination
- Record vital signs

- History and physical examination
- Assess Liver Scores: MELD, Child Pugh and Discriminant Function
- Alcohol consumption history – Timeline Followback Questionnaire
- Assess and record AEs
- Review and record concomitant medications. Confirm that participant is not receiving concomitant systemic corticosteroids.
- Evaluation of compliance
- Obtain blood samples for serum chemistry, hematology and coagulation tests
- Urine pregnancy test in females of childbearing potential
- Assess study medication compliance and perform accountability
- Instruct the patient to take the daily dose of study medication, at the clinic, with water and approximately 30 minutes prior to eating.
- Dispense study medication for at-home dosing and remind the patient to take study medication with water, approximately 30 minutes prior to breakfast. Instruct the patient to swallow the tablet whole; s/he must not chew, divide, or crush the tablet.
- The subject should be reminded that fasting (8 hours) is required prior to his/her next visit. The subject should not take study medication on the morning of the next clinic visit (D28) as s/he will dose at the clinic.
- Perform biosample banking for future use

**6.2.5. Day 21 procedures ( $\pm$  2 days)**

- This consists of a telephone visit where the participant will be inquired about his/her well-being, compliance with IP, concomitant medications and alcohol use.
- The subject should be reminded that fasting (8 hours) is required prior to his/her next visit. The subject should not take study medication on the morning of the next clinic visit (D28) as s/he will dose at the clinic. Confirm that participant is not receiving concomitant systemic corticosteroids.

**6.2.6. D28 Procedures ( $\pm$  2 days) - Must present after at least 8 hours of fasting**

- Perform a physical examination
- Record vital signs
- Alcohol consumption history – Timeline Followback Questionnaire
- Assess and record AEs

- Assess Liver Scores: MELD, Child Pugh and Discriminant Function
- Review and record concomitant medications. Confirm that participant is not receiving concomitant systemic corticosteroids.
- Assess study medication compliance and perform accountability
- Obtain blood samples for serum chemistry, hematology and coagulation tests
- Urine pregnancy test in females of childbearing potential
- Instruct the patient to take the daily dose of study medication, at the clinic, with water and approximately 30 minutes prior to eating
- The subject should be reminded that fasting (8 hours) is required prior to his/her next visit. The subject should not take study medication on the morning of the next clinic visit (D42) as s/he will dose at the clinic.
- Perform biosample banking for future use

**6.2.7. Day 42 Procedures (+ 2 days) - Must present after at least 8 hours of fasting**

- Perform a physical examination
- Record vital signs
- Assess Liver Scores: MELD, Child Pugh and Discriminant Function
- Alcohol consumption history — Timeline Followback Questionnaire
- Assess and record AEs
- Review and record concomitant medications. Confirm that participant is not receiving concomitant systemic corticosteroids.
- Assess study medication compliance and perform accountability and obtain any remaining study medication from patient
- Obtain blood samples for serum chemistry, hematology and coagulation tests
- Perform a urine pregnancy test in females of childbearing potential
- Perform a standard 12-lead electrocardiogram (ECG)
- Obtain blood samples for special investigations as outlined in section 3.2
- Instruct the patient to take the final dose of study medication, at the clinic, with water and approximately 30 minutes prior to eating
- Perform biosample (blood and stool) banking for future use

**6.2.8. Follow up phase D90, D120 and D180 ( $\pm$  2 weeks) – Must present after at least 8 hours of fasting**

- Perform a physical examination
- Record vital signs
- Alcohol consumption history- – Timeline Followback Questionnaire
- Assess and record AEs
- Assess Liver Scores: MELD, Child Pugh and Discriminant Function
- Review and record concomitant medications
- Obtain blood samples for serum chemistry, hematology, and coagulation tests
- Perform biosample banking for future use

**6.2.9. Early Termination Procedures**

Subjects who withdraw consent or discontinue treatment prematurely during the Treatment Phase should complete the assessments required on Day 42. Subjects who discontinue prematurely during the Follow-up Phase should complete the assessments required on Day 180.

**6.2.10. Unscheduled Safety Visits**

The investigator may schedule an at-clinic Unscheduled/Safety Visit at any time if clinically warranted. Unscheduled and/or repeat assessments may be conducted. As appropriate, the designated study physician should be contacted.

**6.2.11. Specimen Banking**

Specimens to be banked include genomic DNA at D0, blood mononuclear cells at D0, D28 and D42, and blood (serum and plasma) samples at D0, D14, D28, D42, D90, D120 and D180. Stool samples collected at D0 and D42 will also be banked for future ancillary studies.

**7. EFFICACY EVALUATIONS**

**TO ASSESS THE EFFECTS OF OCA IN PATIENTS WITH MODERATELY SEVERE AH ON:**

**PRIMARY OBJECTIVE**

- Changes in MELD score at 6 weeks of treatment
- Incidence of SAEs during the treatment phase

## Secondary Objectives

- Any SAEs during the follow-up phase
- SAEs attributable to the study medicine during the treatment and follow-up phases
- AEs and discontinuation rates during the treatment and follow-up phases
- Change in MELD score at 90 and 180 days
- Change in Child-Pugh score at 6 weeks and 90 and 180 days
- Mortality rate at 6 weeks, 90 days and 180 days
- Rates of hospitalization and lengths of stay
- Changes in intestinal inflammation and bacterial translocation
- Changes in serum oxidative stress, cytokines, and activation of innate immunity.

## 8. SAFETY EVALUATIONS

### 8.1. ADVERSE EVENTS

Adverse event (AE) data will be collected from Day 0 through the DB phase, until the patient fully completes her/his trial participation at the Follow Up visit.

### 8.2. PHYSICAL EXAMINATION AND VITAL SIGNS

#### 8.2.1. Physical Examination

To assess for clinical findings, the investigator or designee will perform a physical examination at the time points specified in the Schedule of Trial Procedures (Table 1). This includes height only at Screening. The physical examination must include the following:

- General appearance
- Weight
- Eyes
- Ears, nose, and throat
- Neck
- Respiratory system
- Cardiovascular system
- Abdominal region
- Mental status
- Neurological system

### **8.2.2. Vital Signs**

The following vital signs will be assessed at indicated visits: body temperature, sitting heart rate, and sitting blood pressure (BP). When taking heart rate and BP readings, patients should be seated quietly for a minimum of 3 minutes before the reading is taken. The heart rate should be recorded over a 60 second period.

### **8.3. CLINICAL LABORATORY**

Blood samples for serum chemistry, hematology, and coagulation will be collected at every visit as detailed in the Schedule of Trial Procedures (section 3.2.). The number and volume of samples to be collected at each visit will be detailed in a separate document. These tests will be conducted at local laboratories at 3 participating sites.

All patients with laboratory tests containing clinically significant abnormal values should be followed regularly until the values return to normal ranges, until a valid reason for the AE (other than study medication related AE) is identified, or until further follow up is deemed medically unnecessary.

### **8.4. ELECTROCARDIOGRAM**

Standard 12-lead ECGs will be collected at screening and Day 42 visits. The investigator or designee will review the 12-lead ECG and findings will be recorded in the CRF as normal, abnormal but not clinically significant, or abnormal and clinically significant. Any clinically significant abnormalities on ECGs recorded after Day 0 will also be documented as AEs and entered on the AE page of the CRF.

Investigative sites must retain a copy of all 12-lead ECGs evaluated by the investigator or designee. These ECGs must be clearly labeled with the subject's 5 digit study number, Screening or Randomization Number, date and time. There is no central review of the ECGs. The following variables will be assessed: PR, QRS, QT and QTc intervals and a clinical evaluation for each ECG will be provided.

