### 4.2 INCLUSION CRITERIA

If used, the term 'baseline' (BL) within this protocol, unless otherwise specified, is intended to mean, 'prestudy' or 'pretreatment' (of study medication). It refers to values obtained during the Screening or Day 0 visits, prior to the patient's first dose of study medication.

Patients must meet all of the following criteria to enter the trial.

**(a)** Individuals  $\geq 21$  years with a diagnosis of acute AH. The diagnosis of acute alcoholic hepatitis will be based on clinical features and testing including hepatomegaly, jaundice, fever, leukocytosis, compatible liver biochemistries in the context of heavy alcohol consumption. A liver biopsy is not mandatory, but will be required to confirm the diagnosis if a firm diagnosis of AH cannot be made on clinical and laboratory criteria

**(b)** Moderate severity defined as MELD score > 11 and < 20

**(c)** Heavy alcohol consumption (defined as > 40 grams per day on average in women and > 60 grams per day on average in men for a minimum of 6 months and within the 6 weeks prior to study enrollment)

**(d)** Written informed consent

**(e)** Negative urine pregnancy test where appropriate

**(f)** Women of child bearing potential should be willing to practice contraception throughout the treatment period

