### **9.4. FOLLOW UP OF AEs**

All AEs, including clinically significant laboratory values or physical examination findings relative to pretreatment assessments, must be followed during the trial until

the AE resolves, is no longer of clinical concern, has stabilized or is otherwise explained, or the patient is lost to follow up.

AEs ongoing at the final visit that are deemed to be ‘possibly, probably, or definitely’ related or of other clinical significance must be followed for as long as necessary to adequately evaluate the safety of the patient or until the event stabilizes, resolves, or is no longer of clinical concern. If resolved, a resolution date for the AE should be documented on the CRF. The investigator must ensure that follow up includes any supplemental investigations indicated to elucidate the nature and/or causality of the AE. This may include additional laboratory tests or investigations, or consultation with other healthcare professionals, as considered clinically appropriate by the investigator.

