## 10. STATISTICAL METHODS

### 10.1. ANALYSIS SETS

Primary end point: Analysis will be based on intention-to-treat principle. We will evaluate the main outcome, change in MELD score at day 42, in the framework of the repeated measurements analysis of covariance (ANCOVA) model. Specifically, MELD score at each follow-up visit will be used as the outcome variable. The main predictor is treatment group (GROUP). We will adjust for time (visit) and baseline MELD score and include the interaction between GROUP and visit. The interaction term allows evaluation of GROUP difference at each visit. The main comparison is the differences of MELD score change at day # 28 between two groups. A random intercept will be used to adjust for the correlation among the observations from the same subject. We will also evaluate the GROUP difference at 90 and 180 days in the framework of above repeated ANCOVA model.

SAEs during treatment: The primary analysis is to compare the proportion of patients having at least one SAE during the treatment period between the two groups using Chi-square tests. *SAE during follow-up* will be analyzed similarly. Other safety outcomes include AEs, discontinuations, pre-defined laboratory abnormalities, and predefined EKG abnormalities. Other continuous outcomes will be analyzed in a similar way to MELD score, binary outcomes will be analyzed in a similar way to SAE, and censored time-to-event outcomes will be analyzed using appropriate survival analysis tools (e.g., Kaplan-Meier plots, Cox models).

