#### **10.3.3. Additional Safety and Clinical Findings**

Additional safety assessments include vital signs, physical examinations, and ECGs. Descriptive statistics of the vital sign and ECG parameters will be presented by treatment group and trial visit, as well as the change from BL at each visit. The percentage of patients in each treatment group with clinically significant abnormal ECG findings will be summarized.

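### The AE rule in 8.4 and the ECG percentage in 10.3.3 are not tied to the Screening ECG, so unchanged pre-existing abnormalities dilute the categorical ECG comparison

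*Combined protocol and SAP*

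**What the plan says.** Section 8.4 fixes two time points: "Standard 12-lead ECGs will be collected at screening and Day 42 visits". The site reads each tracing locally, without central review, and records it on a three-level scale: normal, abnormal without clinical significance, or abnormal with clinical significance. The AE rule follows: "Any clinically significant abnormalities on ECGs recorded after Day 0 will also be documented as AEs".

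Section 10.3.3 plans two ECG summaries. The ECG parameters are described by arm and visit, "as well as the change from BL at each visit". Then, for the categorical reading: "The percentage of patients in each treatment group with clinically significant abnormal ECG findings will be summarized". That second sentence names no visit, no baseline category and no shift.

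Three other places bear on the point:

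- The exclusion criteria (4.3) contain nothing about the ECG, and the screening procedures (6.2.1) attach no eligibility consequence to it.
- Section 10.3.1 limits the AE incidence tables to TEAEs, meaning events that are new, more frequent or worse once study medication has started.
- Section 10.1 lists "pre-defined laboratory abnormalities, and predefined EKG abnormalities" among the other safety outcomes and has binary outcomes analysed like SAEs, that is, by chi-square. The documents do not define these ECG abnormalities.

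**The concern.** A patient with a clinically significant abnormality at Screening can be randomized. If the Day 42 tracing shows the same abnormality, the literal rule in 8.4 makes it an AE, and the 10.3.3 percentage counts the patient. A patient with a normal Screening ECG and a new abnormality at Day 42 is counted in the same way. The percentage therefore adds background prevalence to any treatment effect.

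This matters because each patient has only one scheduled on-treatment ECG, and the categorical reading is where rhythm, conduction and ischaemic findings would appear. Mean changes in intervals do not capture these. In arms of about 27 to 30 patients, a few background cases per arm change the ratio noticeably.

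**Working it through.** **Plan figures.** The plan gives no ECG rates and no ECG power, so there is no stated figure to reproduce on this point. The number per arm comes from 10.2: 30 × 0.90 = 27. The 80% power stated there for an effect size of 0.78 reproduces (0.803, t-test, two-sided alpha 0.05 assumed). That dropout figure is for Day 28; 27 is used here for Day 42 as an assumption.

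**Assumed inputs.** Let b be the share in each arm with an unchanged clinically significant abnormality at Screening: 5%, 10% or 20%. Let r be the new-onset rate among the other patients: 20% (OCA) v 2% (placebo), and separately 10% v 2%. Patients with a pre-existing abnormality are assumed not to worsen.

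**Formulas.**

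- Counted as written: b + (1 − b) × r
- Counted as new or worsened, over all evaluable patients: (1 − b) × r
- Risk difference under either count: (1 − b) × (r for OCA − r for placebo), because b cancels
- Background cases per arm: 27 × b, which is 1.35, 2.7 or 5.4

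**Worked case, b = 10%, 20% v 2%.**

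- As written: 0.10 + 0.90 × 0.20 = 28.0% v 0.10 + 0.90 × 0.02 = 11.8%. The difference is 16.2 points and the ratio 2.37.
- New or worsened: 0.90 × 0.20 = 18.0% v 0.90 × 0.02 = 1.8%. The difference is 16.2 points and the ratio 10.
- Standard error of the difference as written: √(0.28 × 0.72/27 + 0.118 × 0.882/27) = 10.6 points.
- Standard error for new or worsened: √(0.18 × 0.82/27 + 0.018 × 0.982/27) = 7.8 points.

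**All cases.** Power is by exact enumeration of the uncorrected Pearson chi-square at two-sided alpha 0.05, 27 per arm.

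| New onset | b | Ratio as written | Ratio, new or worsened | Risk difference, both counts | Power as written | Power, new or worsened |
|---|---|---|---|---|---|---|
| 20% v 2% | 5% | 3.48 | 10 | 17.1 points | 44.6% | 60.4% |
| 20% v 2% | 10% | 2.37 | 10 | 16.2 points | 34.3% | 57.0% |
| 20% v 2% | 20% | 1.67 | 10 | 14.4 points | 22.6% | 49.5% |
| 10% v 2% | 5% | 2.10 | 5 | 7.6 points | 15.0% | 16.2% |
| 10% v 2% | 10% | 1.61 | 5 | 7.2 points | 12.2% | 14.5% |
| 10% v 2% | 20% | 1.30 | 5 | 6.4 points | 9.2% | 11.3% |

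The fair comparison is between the two counts at the same b. With no pre-existing cases, power would be 63.6% (20% v 2%) or 17.9% (10% v 2%). Measuring the loss from there would overstate it, because part of the drop remains under the better count: fewer patients are then at risk of a new finding.

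**The case against.** The strongest reply is that the plan already looks back to the pre-treatment state in two places, and this largely stands. Section 8.4 says: "The following variables will be assessed: PR, QRS, QT and QTc intervals and a clinical evaluation for each ECG will be provided". Section 10.3.3 reports ECG parameters as change from baseline, and 4.2 says of baseline: "It refers to values obtained during the Screening or Day 0 visits". For the ECG that can only be the Screening tracing. A reader might infer that the plan never compares the ECG with Screening; that is not so, and a newly prolonged QT would show in the interval summaries. The TEAE definition in 10.3.1 likewise keeps an unchanged abnormality out of the AE incidence tables. What remains outside both filters is the categorical percentage and the raw AE record.

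A reader might also see a contradiction with 9.1.1, which lists worsening of an existing condition as an AE, or with 9.4, which judges "clinically significant laboratory values or physical examination findings relative to pretreatment assessments" and does not name the ECG. Neither is a true conflict. The 9.1.1 list is expressly open-ended, and the findings named in 9.4 are given as inclusions among all AEs to be followed. Broad capture at the site with a later TEAE filter is a coherent approach.

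Nor is the information lost. The Screening reading is on the CRF on the same scale, and AEs are recorded by diagnosis, so new and old findings can be separated afterwards. The defect lies in the planned count.

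Finally, randomization balances pre-existing findings in expectation. That is correct, and it is why the expected risk difference is the same under both counts. It does not guarantee balance in one small trial. With 27 per arm, the chance that the arms differ by three or more pre-existing cases is about 25% at b = 10% and 39% at b = 20%.

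**Conclusion.** The point holds as a minor one about safety reporting. As written, an unchanged Screening abnormality can be logged as an AE and counted in the ECG percentage alongside new ones. The result is a diluted ratio and a less precise comparison.

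It would be too strong to say that the rule masks a drug effect. The expected risk difference is unchanged, and the interval summaries and TEAE tables remain. The size depends on a prevalence that the documents do not give: in the illustration the rule costs about 16 to 27 points of power at 20% v 2%, but only about 1 to 2 points at 10% v 2%.

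It would also be too strong to say that a planned chi-square test uses this category. The ECG abnormalities in 10.1 are undefined and are not shown to be the clinically significant category of 8.4. Section 10.3 treats safety data descriptively, so the power figures serve mainly to show the loss of precision. Neither primary endpoint nor the sample size is touched.

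**What to change.** In 8.4, record as AEs those clinically significant ECG abnormalities after Day 0 that are new or worse than on the Screening ECG, in line with the TEAE definition in 10.3.1.

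In 10.3.3, present a Screening-to-Day 42 shift table by arm on the existing three-level scale, and base the percentage on patients with a new or worsened clinically significant abnormality. Define the ECG abnormalities meant in 10.1; if they use this category, apply the same basis to any test.

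The cost is a short qualifier in 8.4, a definition in 10.1 and one changed table. No visit, tracing or patient is added, because the Screening ECG is already collected and classified. The small downside is that the reference tracing may be up to 8 weeks before Day 0, so a change arising in that interval would count as new.
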